6.4. Study Intervention Compliance

Participant compliance with study intervention will be assessed at each visit by delegated site personnel. Compliance will be assessed by combination of counting returned tablets and

discussion with the participant during the site visits and documented in the source documents and CRF. Deviation(s) from the prescribed dosage regimen should be recorded in the CRF.

A record of the number of abrocitinib tablets dispensed to and taken by each participant must be maintained and reconciled with study intervention and compliance records. Intervention start and stop dates, including dates for intervention delays and/or dose reductions, will also be recorded in the CRF.

The following compliance cases will be considered medication errors and will be discussed with the sponsor for possible withdrawal from the study:

- Participants administering >8 tablets in 1 day or administering ≥4 tablets/day for 4 consecutive days;
- Participants who have an overall compliance of <80% or >120% between visits for oral study intervention;

Any deviation from protocol specified dosing should be recorded as a protocol deviation and the investigator or designee is to counsel the participant and parent(s)/legal guardian (if applicable) and ensure steps are taken to improve compliance. In addition, if the compliance deviation reaches the thresholds defined above it should also be recorded as a medication error (see Section 8.3.10).

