7. DISCONTINUATION OF STUDY INTERVENTION AND PARTICIPANT DISCONTINUATION/WITHDRAWAL

7.1. Discontinuation of Study Intervention

It may be necessary for a participant to permanently discontinue study intervention. Reasons for permanent discontinuation of study intervention include the following:

- Other AE, per judgment of the investigator, requiring discontinuation from treatment (or, if necessary/desired, following discussion with sponsor).
- Pregnancy.
- Serious infection must result in temporary interruption of study intervention. Study intervention cannot be restarted until the serious infection has resolved and restarting study intervention has been discussed and agreed with the medical monitor. If the participant cannot be restarted on study intervention within 28 days, or the infection is not resolved, or there is no agreement received from the medical monitor to restart study intervention, then the participant must be permanently discontinued from study intervention.
- Any bleeding event thought to be associated with a platelet count reduction per the judgement of the investigator (or, if necessary/desired, following discussion with sponsor).
- Any AE or laboratory abnormality, that per the investigator's judgement requires temporary interruption to dosing of study intervention for >28 days.
- Any AE of venous thromboembolism.
- Participants who have recurrent SIB during the trial must be discontinued from the study and treated appropriately. If a participant endorses a 4 or 5 on the ideation subscale or any behavioral item of the C-SSRS on 2 occasions and is confirmed to have active SIB on both occasions by a risk assessment conducted by a qualified MHP, then the participant must be discontinued from the study and treated appropriately.
- Estimated Creatinine Clearance <60 mL/min using the Cockcroft-Gault method.

Note that discontinuation of study intervention does not represent withdrawal from the study. If study intervention is permanently discontinued, the participant will remain in the study to be evaluated for end of treatment and end of study/follow-up assessments. See the SoA for

PFIZER CONFIDENTIAL

data to be collected at the time of discontinuation of study intervention and follow-up for any further evaluations that need to be completed.

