7.2. Participant Discontinuation/Withdrawal From the Study

A participant may withdraw from the study at any time at his/her own request. Reasons for discontinuation from the study include the following:

- Refused further study procedures;
- Lost to follow-up;
- Death;
- Study terminated by sponsor;
- Behavioral, compliance or administrative reasons.

At the time of discontinuing from the study, if possible, an early discontinuation visit should be conducted. See the SoA for assessments to be collected at the time of study discontinuation and follow-up and for any further evaluations that need to be completed.

If a participant withdraws from the study, he/she may request destruction of any remaining samples taken and not tested, and the investigator must document any such requests in the site study records and notify the sponsor accordingly.

If the participant withdraws from the study and also withdraws consent (see Section 7.2.1) for disclosure of future information, no further evaluations should be performed and no additional data should be collected. The sponsor may retain and continue to use any data collected before such withdrawal of consent.

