7.2.1. Withdrawal of Consent

Participants who request to discontinue receipt of study intervention will remain in the study and must continue to be followed for protocol-specified follow-up procedures. The only exception to this is when a participant specifically withdraws consent for any further contact with him or her or persons previously authorized by the participant to provide this information. Participants should notify the investigator in writing of the decision to withdraw consent from future follow-up, whenever possible. The withdrawal of consent should be explained in detail in the medical records by the investigator, as to whether the withdrawal is only from further receipt of study intervention or also from study procedures and/or posttreatment study follow-up, and entered on the appropriate CRF page. In the event that vital status (whether the participant is alive or dead) is being measured, publicly available information should be used to determine vital status only as appropriately directed in accordance with local law.

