8.3.1. Time Period and Frequency for Collecting AE and SAE Information

The time period for actively eliciting and collecting AEs and SAEs ("active collection period") for each participant begins from the time the participant provides informed consent, which is obtained before the participant's participation in the study (ie, before undergoing any study-related procedure and/or receiving study intervention), through and including a minimum of 28 calendar days, except as indicated below, after the last administration of the study intervention.

Follow-up by the investigator continues throughout and after the active collection period and until the AE or SAE or its sequelae resolve or stabilize at a level acceptable to the investigator.

For participants who are screen failures, the active collection period ends when screen failure status is determined.

If the participant withdraws from the study and also withdraws consent for the collection of future information, the active collection period ends when consent is withdrawn.

If a participant permanently discontinues or temporarily discontinues study intervention because of an AE or SAE, the AE or SAE must be recorded on the CRF and the SAE reported using the CT SAE Report Form.

Investigators are not obligated to actively seek information on AEs or SAEs after the participant has concluded study participation. However, if the investigator learns of any SAE, including a death, at any time after a participant has completed the study, and he/she considers the event to be reasonably related to the study intervention, the investigator must promptly report the SAE to Pfizer using the CT SAE Report Form.

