9.1. Statistical Hypotheses

9.1.1. Estimands

9.1.1.1. Primary Estimand

The primary estimand is defined by the following attributes:

Population: Patients aged 12 years and older with moderate to severe AD.

Variable: Binary indicator of whether any AE/SAE occurred at least once.

Treatment condition: The randomized intervention regardless of intercurrent events.

The intercurrent events "intervention discontinuation for any reason" and "intervention compliance" are both addressed by the treatment condition of interest.

Population-level summary: Incidence rate of AEs/SAEs, defined as the number of participants with AEs/SAEs from the time of first dose to Week 16 divided by the number of participants, in each treatment arm.

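### Dosing non-compliance alone can take a participant out of the study, although the primary safety estimand disregards compliance; the effect is probably small and the fix is cheap

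*Protocol*

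**What the plan says.** **The rule.** Protocol 6.4 names two kinds of dosing deviation: taking more than 8 tablets in a day or at least 4 a day for 4 days running, and compliance under 80% or over 120% between visits. These cases "will be considered medication errors and will be discussed with the sponsor for possible withdrawal from the study". The same section also tells the investigator to counsel the participant and work to improve compliance. Protocol 7.2 lists "Behavioral, compliance or administrative reasons" as grounds for leaving the study, as an item separate from refusal, loss to follow-up, death and termination by the sponsor. On exit, 7.2 says: "At the time of discontinuing from the study, if possible, an early discontinuation visit should be conducted".

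**How people who stop drug are treated.** Under 7.1, if drug is stopped permanently, "the participant will remain in the study to be evaluated for end of treatment and end of study/follow-up assessments". Section 7.2.1 adds: "Participants who request to discontinue receipt of study intervention will remain in the study and must continue to be followed for protocol-specified follow-up procedures".

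**The estimand.** Protocol 9.1.1.1 has "Treatment condition: The randomized intervention regardless of intercurrent events" and names compliance as one of those events. SAP 2.1.1 and 6.1.1 call this treatment policy, use all collected data and impute nothing.

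**Adverse event collection.** Protocol 8.3.1 runs active collection "through and including a minimum of 28 calendar days, except as indicated below, after the last administration of the study intervention". It also says: "Investigators are not obligated to actively seek information on AEs or SAEs after the participant has concluded study participation".

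**The concern.** A treatment-policy estimand needs data after the intercurrent event. Here the event is non-compliance, and the protocol allows it to end study participation, even for someone willing to stay. A non-adherent participant can then have weaker assured follow-up than someone who simply asks to stop the tablets.

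The group is unlikely to be a random one. The protocol expects that serious infection, COVID-19 or other adverse events may interrupt dosing (7.1, 10.8.4), and 6.4 does not say whether such interruptions count against compliance. Participants who leave stay in the Safety population denominator, and missing values are not imputed (SAP 3.1, 4 and 6.1.1), so an event that is never collected counts as no event. Any distortion would make the drug look safer.

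The scheduled safety data are also sparse, so a missed end-of-treatment visit matters for the individual record: the only post-baseline ECG and complete physical examination are done there.

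**Working it through.** **1. The plan's own precision figure.** Protocol 9.5 gives a maximum margin of error of 10% with 100 per arm. The normal-approximation half-width at a proportion of 0.5 is 1.96 × √(0.25/100) = 9.8 points. The figure reproduces and is not in dispute; it serves as the yardstick below.

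**2. When the discussion is triggered.** Visits fall on Days 1, 15, 29, 57 and 85, so the intervals are 14, 14, 28 and 28 days with one dose a day.
- 14 days: 2 missed gives 12/14 = 85.7%; 3 missed gives 11/14 = 78.6%, below 80%.
- 28 days: 5 missed gives 23/28 = 82.1%; 6 missed gives 22/28 = 78.6%, below 80%.
- Upper limit: 3 extra doses on 14, or 6 on 28, give 121.4%.

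This shows when the discussion starts. It does not show how often anyone leaves.

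**3. Who is mainly affected.** Three groups are better covered: intake above 8 tablets in 24 hours (6.7, at least 28 days of monitoring), clinically significant treatment-emergent abnormalities at withdrawal (7.1), and adolescents (10.10.4, MRI and an end-of-study visit). That leaves mainly adults outside 80% to 120%, or taking at least 4 tablets a day for 4 days without exceeding 8 in 24 hours.

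**4. Scheduled data at risk.** The main Schedule of Activities has one post-baseline ECG (Week 12) and two post-baseline laboratory sets (Weeks 4 and 12). For an adult withdrawn at the visit where non-compliance is found, with no exit visit held:
- Week 2: 0 of 1 ECGs, 0 of 2 laboratory sets.
- Week 4 or Week 8: 0 of 1 ECGs, 1 of 2 laboratory sets.

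These values would be missing from the summaries in SAP 6.6.2 and 6.6.4. If the exit visit in 7.2 is held with the end-of-treatment assessments, they are not lost.

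**5. Adverse event coverage.** SAP 3.1 counts events that start before last dose plus 28 days. With last dose on Day d, the window is Days 1 to d + 27, or d + 27 days. If collection follows the 28-day rule of 8.3.1, no days are uncovered. If a site stopped on the day of withdrawal, 27 days would be:
- Week 2 (d = 15): 27/42 = 64%.
- Week 4 (d = 29): 27/56 = 48%.
- Week 8 (d = 57): 27/84 = 32%.

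These percentages are the worst case under the weaker reading of 8.3.1.

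**6. Effect on the primary result.** The documents give no withdrawal rate. If k of 100 per arm are withdrawn, incidence can fall by at most k/100. For an assumed k of 1 to 5, that is 1 to 5 points, and only if each person's sole event starts after withdrawal and is never collected.

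A less extreme illustration assumes 5% withdrawn, a true 16-week incidence of 60% and a constant hazard λ = −ln(0.4)/16 = 0.0573 per week. The observed rate is 0.95 × 0.60 + 0.05 × (1 − e^(−λt)), where t is the number of weeks of collection.
- Withdrawn at Week 2: 57.5% with no later collection (t = 2), 58.5% with 28 more days (t = 6).
- Withdrawn at Week 8: 58.8% (t = 8), 59.5% (t = 12).

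Losing the 28-day follow-up thus costs under 1 point here (57.54% against 58.45% at Week 2; 58.84% against 59.49% at Week 8). The remaining gap to 60% arises because 28 days after an early last dose falls short of Week 16. That gap is separate from the present point.

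**The case against.** The strongest reply is that a willing participant found non-compliant at a clinic visit is already on site. The exit visit is then possible, 7.2 says that it should be done, and its next sentence points to the Schedule of Activities for assessments at discontinuation and follow-up. The data losses in step 4 therefore suppose that 7.2 was not followed. This largely stands. A reader might infer that the exit visit is a mere option; the wording is stronger than that, though it does not guarantee the visit or the later end-of-study contact.

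A reader might also infer that adverse event collection stops at withdrawal, so that a third to two thirds of the window is lost. The documents do not support this as the natural reading. Section 8.3.1 names only two early ends, screen failure and withdrawal from the study combined with withdrawal of consent. The second condition would be redundant if leaving the study were enough. The sentence about concluded participation pulls the other way and leaves some ambiguity.

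A third inference is that the sponsor may remove people at will. Section 6.4 provides only for discussion and possible withdrawal, names no decision-maker, and asks for counselling as well.

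Finally, compliance in 7.2 may cover visits and procedures too, so deleting the word would go too far. That is correct, and the fix below keeps it.

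**Conclusion.** The point holds as a mismatch between a stated rule and the estimand: dosing non-compliance alone may lead to study withdrawal, although the primary estimand disregards it and people who stop drug are kept in. It is a cheap improvement, not a threat to the trial.

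The likely effect is small. On the better reading of 8.3.1, no treatment-emergent days are lost. At an assumed 1 to 5 withdrawals per arm, at most 1 to 5 end-of-treatment ECGs are missing, and the primary incidence moves by at most 1 to 5 points in the extreme case, against a planned margin of 10. The analyses are descriptive (SAP 5.1), and the responder endpoints already count discontinuers as non-responders.

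A reader might conclude that the primary safety result is materially biased. The documents do not support that: they give no withdrawal frequency, and every figure for the size of the effect rests on an assumed one. What is lost is assurance of the end-of-treatment and end-of-study data and of unambiguous adverse event follow-up, mainly in non-adherent adults.

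**What to change.** - **Protocol 6.4:** make the outcome of the sponsor discussion *possible discontinuation of study intervention* instead of study withdrawal. Whether drug is stopped remains a case-by-case decision.
- **Protocol 7.2:** keep compliance as a reason for non-dosing matters such as visits and procedures, and add: *Dosing non-compliance alone is not a reason for withdrawal from the study; these participants complete the EOT and EOS assessments and AE collection to at least 28 days after last dose (Section 8.3.1) unless they withdraw consent.*

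This applies the protocol's own 7.1 rule to non-adherent participants. It changes no sample size, procedure or SAP text. It does not by itself extend follow-up to Week 16 for someone who stops early.

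The cost is up to two already scheduled visits for some non-adherent participants, who may still miss them. The change also needs an amendment with IRB/EC approval, and health authority approval if it is judged substantial (10.1.1), so it is best bundled with the next amendment.

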6.5. Dose Modification

Dose modification is not allowed in this study.

6.6. Continued Access to Study Intervention After the End of the Study

No intervention will be provided to study participants at the end of their study participation. Investigator may consider alternative forms of therapy for their participant until abrocitinib is potentially available.

6.7. Treatment of Overdose

For this study, any dose of study intervention greater than 8 tablets within a 24-hour time period (± 2 hours) will be considered an overdose.

There is no specific treatment for an overdose.

In the event of an overdose, the investigator should:

- 1. Contact the medical monitor within 24 hours.
- 2. Closely monitor the participant for any AEs/SAEs and laboratory abnormalities for at least 5 half-lives or 28 calendar days after the overdose of study intervention (whichever is longer). Closely monitor the participant for any AEs/SAEs.

- 3. Document the quantity of the excess dose as well as the duration of the overdose in the CRF.
- 4. Overdose is reportable to Pfizer Safety only when associated with an SAE.
- 5. A plasma sample for PK analysis may be requested by the Pfizer clinician (determined on a case-by-case basis).

Decisions regarding dose interruptions or modifications will be made by the investigator in consultation with the medical monitor based on the clinical evaluation of the participant.

6.8. Concomitant Therapy

Any medication or vaccine (including over-the-counter or prescription medicines, vitamins, and/or herbal supplements) that the participant is receiving at the time of enrollment or receives during the study must be recorded along with:

- Dates of administration including start and end dates
- Dosage information including dose and frequency

The Pfizer clinician should be contacted if there are any questions regarding concomitant or prior therapy.

Hormonal contraceptives that meet the requirements of this study are allowed to be used in participants who are WOCBP (refer to Appendix 4).

Participants will abstain from all prohibited concomitant medications as described in Section 6.8.2 and Appendix 7. Medications that are taken in the Screening period (after informed consent is obtained and before the first dose of study intervention) will be documented as prior medications. Medications taken after the first dose of study intervention will be documented as concomitant medications. All concomitant medications taken during the study must be recorded in study records with indication (if AD), reference to any associated adverse event, dose, and start and stop dates of administration. Participants will be queried about concomitant medications and treatments, and vaccinations) at each study visit. Any new concomitant medications or dose changes to current concomitant medications should prompt evaluation for potential new or worsening adverse events.

Unless prohibited by the protocol, participants may be administered any other medications necessary for the treatment of medical disorders as deemed necessary by the treating physician. Following Day 1, the addition of concomitant medications or any change in the dosage should be limited to those considered medically essential.

The concomitant medication for any reason must be a locallyapproved medication and dose.

Participants should report any changes to medications during the study to the investigator as soon as they occur. Medication changes must be documented in the participant's record and eCRF.

6.8.1. Permitted Concomitant Treatments

The following concomitant AD therapies are permitted during the study:

- Oral antihistamines;
- Non-medicated emollients and all topical medications for AD at the discretion of the investigator and in accordance with their usual practice.

The following concomitant medications are permitted during the study:

- Corticosteroid inhalers and intranasal sprays are permissible for participants receiving a stable dose;
- Ophthalmic corticosteroids are permissible for participants receiving a stable dose;
- Hormonal contraceptives that meet the requirements of this study are allowed to be used in participants who are WOCBP (Refer to Appendix 4);
- Dietary supplements (defined as vitamins and minerals, and purified food substances) of standard potency are allowed in amounts not known to be associated with adverse effects (such as hyper-vitaminosis).

6.8.2. Prohibited Medications and Treatments

Participants are required to discontinue and avoid using certain medications and treatments (refer to Inclusion Criteria [Section 5.1], Exclusion Criteria [Section 5.2], and Appendix 7). Participants should be instructed at each visit to contact the study site investigator promptly if there are any intended changes or additions to concomitant medications.

Participants who received prior treatment with systemic JAK inhibitors are to be excluded from the study. Prior treatment with topical JAK inhibitors is not exclusionary.

Restrictions on certain vaccinations are described in Section 5.3.3.

The Pfizer study team is to be notified of any prohibited medications taken during the study. After consulting with the Pfizer medical monitor, the investigator will make a judgement on the ongoing eligibility of any participant with prohibited medication use during the study.

6.8.3. Rescue Medicine

After Week 4 if medically necessary, participants with intolerable AD symptoms may receive locally-approved rescue therapy with systemic corticosteroids for up to 14 days at a time, at the investigator's discretion, according to local product label. Participants receiving systemic rescue therapy may continue to receive abrocitinib concurrently and should

continue study visits and assessments. Rescue therapy will be obtained locally and administration must be recorded on the CRF. As possible, investigators should conduct safety and efficacy assessments (eg, safety labs, disease severity scores) before administering rescue therapy. An unscheduled visit may be used for this purpose, if necessary.

